6. INCLUSION AND EXCLUSION CRITERIA*

Child eligibility criteria for enrollment in Asthma Link™ (established clinical program):

- (1) children aged 6-17 years (enrolled in grade 1-12)
- (2) prescribed daily inhaled corticosteroid (ICS) for asthma;
- (3) 1 or more courses of oral steroids in the past 2 years OR 1 or more hospitalizations or ED visits for asthma in the past 2 years OR Asthma Control Test (ACT) score <19 OR 1 or more sick or urgent care visits for asthma (including telehealth) in the last year
- (4) parent/child report of poor ICS adherence on adherence checklist- i.e. child or parent says “Yes” when provider asks if they have difficulty remembering to take their medication or if they regularly take medication holidays or breaks;
- (5) able and willing to assent;
- (6) parental permission
- (7) English or Spanish speaking.

STUDY INCLUSION/EXCLUSION Criteria:

Child Inclusion criteria:

- 1) Meet the eligibility criteria for Asthma Link (as described above) with exception to (7)
- 2) Enrolled in Asthma Link™ (if randomized to the Asthma Link™ Condition)
- 3) Able and willing to provide informed assent
- 4) Must be English or Spanish speaking

Child Exclusion criteria:

- (1) Unable or unwilling to provide informed assent
- (2) Diagnosis of a serious co-morbid illness during the past 5 years
- (3) Developmental delay that would prevent study participation.
- (4) Planning on moving from primary residence or moving outside of the school district in the next 1 year
- (5) A sibling to a child participating in this study

Parent Inclusion criteria are:

- 1) Parent/guardian to patient
- 2) 18 years or older
- 3) Able to understand and communicate in English or Spanish

INVESTIGATOR STUDY PLAN

- 4) Able and willing to provide informed consent.
- 5) May or may not be or become pregnant

Medical Provider Inclusion criteria are:

- 1) Able and willing to provide informed consent

Medical Provider Exclusion criteria are:

- 1) Unable or unwilling to provide informed consent

School Nurse Inclusion criteria are:

- 1) Able and willing to provide informed consent

School Nurse Exclusion criteria are:

- 1) Unable or unwilling to provide informed consent

Asthma Champion Inclusion criteria are:

- 1) Able and willing to provide informed consent

Asthma Champion Exclusion criteria are:

- 1) Unable or unwilling to provide informed consent

Adults lacking capacity and prisoners are also excluded

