We anticipate that recruitment of n=72 dyads will take 18 months based on [name] FITLINE study ¹⁸. We do not anticipate issues with this recruitment based on prior recruitment of families for Asthma Link™ from the Worcester community in our pre/post study and based on prior recruitment from these same pediatric practices in the FITLINE study. (also see page 19 which describes estimated number of asthmatics in proposed Pediatric practices, demonstrating feasibility of recruitment). The Institutional Review Board will review all research procedures and protocols. All instruments will be submitted to the IRB for review and approval prior to use.

We will not enroll any participants in the study prior to receiving IRB approval.

SURVEY – PARENT AND CHILD – 20 MINUTES _See uploaded parent baseline, parent 3 month, parent 6 month, and parent 12 month surveys.

The 4 parent surveys will include the following constructs: Patient Health Outcome questions including the Asthma Control Test (ACT; measure of severity of asthma symptoms) and the Maximum Asthma Symptom Days (MSD), Emergency Department visits, hospital admissions, school absences, oral steroid usage and pharmacy refill data. The Baseline survey will include demographic questions that ask about the parent's age, sex, race/ethnicity, relation to the child participating in the study, education, marital status, tobacco usage, health insurance, contact information, family functioning, comorbidities, income, and average monthly as a proxy for socioeconomic status. The 3 month, 6 month, and 12 month follow up surveys for the Asthma Link™ condition will also include the following constructs: acceptability, cost, and sustainability. All surveys will be completed either on-line using RedCap (Please see data management) or over the phone with the Research Coordinator. We are using emails and/or phone calls to deliver/collect these surveys. As soon as the baseline survey has been completed, those completing the survey via email will be automatically sent out future surveys.

SURVEY – SCHOOL NURSE – 10 MINUTES _See uploaded school nurse baseline and end-of-intervention surveys.

The school nurse survey will include the following constructs: acceptability, cost, and sustainability. All surveys will be completed either on-line using RedCap (Please see data management section) or over the phone with the research coordinator. We are using emails and/or phone calls to deliver and collect these surveys.

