SURVEY – MEDICAL PROVIDER – 5 MINUTES _See uploaded medical provider baseline and end-of-intervention surveys. The medical provider survey will include the following constructs: acceptability, cost, and sustainability. All surveys will be completed either on-line using RedCap (please see data management section) or over the phone with the research coordinator. We are using emails and/or phone calls to deliver and collect these surveys.

SURVEY- ASTHMA CHAMPION- 5 MINUTES _See uploaded asthma champion baseline and end-of-intervention surveys. This will include the same constructs of acceptability, cost and sustainability. Surveys will be completed either on-line using RedCap (please see data management section) or over the phone with the research coordinator. We are using emails and/or phone calls to deliver and collect these surveys.

INVESTIGATOR STUDY PLAN

We will be accessing the practice's medical record system (same system as above, e.g., Epic) to obtain documentation of the child's emergency room visits, hospital admissions, and oral steroid courses at the baseline time point (recording the number of events for the 6 months prior), 3 month, 6 month, and 12 month time points (recording the number of each of these events for the 3 or 6 months prior.). This data will also be collected 12 months following the completion of the 12 month survey in order to observe for sustained impact on health outcomes and to see if engagement in Asthma Link continues beyond one year. This data will be directly put into the RedCap database without any downloading of information. (please see data management section)

We will be contacting the child's pharmacy to obtain refill history of their daily ICS medication at baseline (obtaining the number of refills for the prior 6 months), 3, 6, and 12 months, and 12 months following the completion of the 12 month survey to assess for medication adherence. This data will be entered directly into the REDCap database.

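### Baseline ED visits, admissions and steroid courses are counted over 6 months but follow-up over 12; a 12-month baseline would be more informative at almost no cost

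*Combined protocol and SAP*

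**What the plan says.** Section 11 (Procedures Involved) takes ED visits, admissions and oral steroid courses from the practice's record system "at the baseline time point (recording the number of events for the 6 months prior". The same events are then collected at the "3 month, 6 month, and 12 month time points (recording the number of each of these events for the 3 or 6 months prior". A further collection is planned: "This data will also be collected 12 months following the completion of the 12 month survey". The pharmacy refill baseline uses the same half-year, "obtaining the number of refills for the prior 6 months".

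On entry, Section 11 states: "We anticipate that recruitment of n=72 dyads will take 18 months". Section 6, criterion (3), offers several alternative routes to eligibility. One is "1 or more courses of oral steroids in the past 2 years", and hospitalizations and ED visits have the same 2-year look-back. Another is "1 or more sick or urgent care visits for asthma (including telehealth) in the last year". A third is a low Asthma Control Test score, which needs no event history.

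Section 13 (Statistical Analysis) compares the arms by t-test, a nonparametric test or Poisson regression, depending on the distribution. It names no baseline covariate, no offset and no term for season, and it describes the health-outcome analyses as exploratory.

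**The concern.** The baseline window is half the length of the follow-up window. These events are likely to be few per child, so a 6-month count will often be zero even in a child with real underlying risk. A child who qualified on a steroid course 7 or more months earlier can enter with a baseline of zero.

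The baseline matters more here than in an individually randomized trial. Four practices are allocated, matched on size and percent minority and not on asthma severity. Children are then recruited by providers who know their practice's condition, with different scripts in the two arms (Section 11, steps 3 and 3a). Exam-room flyers and triage reminders for the program are used at intervention sites only (Section 24). Prior event history is one of the main ways to check whether the arms recruited similar children, and it is the natural covariate if an event comparison is adjusted.

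Entry is spread over 18 months. If asthma events vary by season, a 6-month count also reflects the month in which the child joined.

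**Working it through.** **Windows.** Follow-up counts cover months 0-3, 3-6 and 6-12: 3 + 3 + 6 = 12 months, against 6 at baseline. Section 9 gives an individual's participation as 6 months, but Sections 11, 13 and 25 all run to 12 months. I take 12.

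**No plan figure to reproduce.** Section 13 gives no event rate, effect size or power that depends on the baseline window. Event rates and between-child variation below are therefore assumptions, shown over a range.

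**Information in the baseline count.** Let each child have a yearly event rate drawn from a gamma distribution with mean λ and variance v = (CV × λ)², with Poisson counts given that rate. The squared correlation between a baseline count over T years and the count over the next 12 months is

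R² = (T·v)² / [(λ·T + T²·v)(λ + v)].

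Central case, λ = 1, CV = 1, so v = 1:

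- T = 0.5: 0.25 / (0.75 × 2) = 0.167
- T = 1: 1 / (2 × 2) = 0.250

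Low end, λ = 0.5, CV = 0.7, so v = 0.1225:

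- T = 0.5: 0.00375 / (0.2806 × 0.6225) = 0.02
- T = 1: 0.01501 / 0.6225² = 0.04

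High end, λ = 1.5, CV = 1.4, so v = 4.41:

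- T = 0.5: 4.862 / (1.8525 × 5.91) = 0.44
- T = 1: 19.448 / 5.91² = 0.56

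The ratio of the two R² values simplifies to (2λ + v)/(λ + v), which always lies between 1 and 2. In the central case it is 3/2. So under this model the longer window is always more informative, whatever the rate.

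**Practical gain.** In the central case the child-level residual SD after adjustment falls by a factor of √(0.75/0.833) = 0.949, or about 5%.

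**Season (assumed).** Suppose the event rate follows a yearly sinusoid of relative amplitude A, with entry dates uniform over the year. The expected 6-month count then ranges over 1 ± 2A/π of its average.

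| A | Range relative to average | Highest/lowest | Correlation of 6-month baseline with 12-month follow-up (λ = 1, CV = 1) |
|---|---|---|---|
| 0 | 1.00 | 1.00 | 0.408 |
| 0.3 | 0.81-1.19 | 1.47 | 0.406 |
| 0.6 | 0.62-1.38 | 2.24 | 0.399 |

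Season can move an individual child's expected count noticeably, but it hardly changes the correlation with a 12-month follow-up count. What limits that correlation is the sparse count and the short window. Season matters more for half-year comparisons. At A = 0.6 (simulated), the baseline correlates 0.27 with months 0-6 and 0.36 with months 6-12, which fall in the same calendar months as the baseline. A 12-month baseline removes the seasonal effect under this model.

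**The case against.** The strongest reply is that the plan never says it will use the baseline count as a covariate. That is correct: Section 13 names none. A reader might infer that a stated adjusted analysis is undermined, and the documents do not support that.

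A reader might also infer that season makes the baseline a weak covariate. The documents do not mention season, and the table shows that even a strong assumed pattern lowers the correlation only from 0.408 to 0.399. Nor is weakness as such established, since the 6-month R² runs from 2% to 44% over the assumed range. Season would bias the arm comparison only if entry dates differ by arm. The intervention-only flyers and triage reminders in Section 24 make a difference possible, but nothing in the plan shows one. Otherwise season adds noise.

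A third tempting reading is that eligibility already requires 2 years of event history for every child. It does not, because criterion (3) is a list of alternatives. Eligibility and baseline windows also serve different purposes and need not match.

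The 6-month window has some logic of its own. It equals the refill baseline and the first two follow-up windows combined, and months 6-12 give a season-matched comparison. A Poisson offset can handle unequal window lengths. These points stand, but an offset corrects length only and adds no information to a sparse count, and the season match leaves months 0-6 and the 12-month total unmatched.

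Finally, a longer history may already be within reach. Section 11, step 1, collects event counts at screening with no window stated, and the coordinator later obtains discharge summaries and emergency service records. That is a reason the change is cheap, but no 12-month count is specified.

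**Conclusion.** The point holds as a cheap improvement of small consequence. The 6-month baseline against 12 months of follow-up is in the text, and under the gamma-Poisson assumption a 12-month baseline is always more informative: R² 0.25 against 0.17 in the central case, 0.04-0.56 against 0.02-0.44 over the assumed range. The size depends on event rates and between-child variation that the documents do not give, and the gain in residual SD is only about 5% in the central case. With two practices per arm, between-practice variation also limits what any child-level covariate can achieve.

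What is limited is the description of arm comparability and any adjusted exploratory event comparison. Recruitment, retention and fidelity, the primary outcomes in Section 4, do not depend on this window, and the sample size in Section 13 rests on feasibility. The documents do not support calling this an error in a planned analysis or a demonstrated bias.

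**What to change.** In Section 11, for both arms and from the record review already planned, record ED visits, admissions and oral steroid courses for the 12 months before entry in two 6-month blocks: the planned 6 months and the 6 before. The planned 6-month count is kept.

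In Section 13, state that the 12-month count will describe the arms at baseline and will be the baseline covariate in the exploratory event-count models, with an offset for follow-up time.

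The cost is one extra field per event type and a few minutes per record, for up to 100 children (Section 25). It should be done before study completion, when Section 14 has the link between identifiers and data destroyed.

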10. STUDY ENDPOINTS*

Please see below table describing the primary and secondary outcome measures

SN=School Nurse

MP=Medical Provider

AC=Asthma Champion

Study Assessments, Measures and Data Collection Timing

Variable	Measure/Instrument
Designed for and Delivered to pediatric practice staff, school staff, and parent-child dyads Administered by Research coordinator	
AIM 1: Primary Feasibility Outcomes for Asthma Link™ research protocol (cluster RCT)	

INVESTIGATOR STUDY PLAN

Participation/Recruitment	# of screened and eligible participants; # refusing to participate; reason(s) for refusal
Retention	# of dropouts; subjects lost to follow-up; reason(s) for dropping out
Program usage/Intervention Fidelity (degree to which using program)	
 Checklist for pediatric practice staff to assess % of eligible children enrolled (see Pedi Practice checklist) School nurse report of % enrolled students receiving supervised therapy (see SN checklist) School nurse checklist of each enrolled child attending daily school nurse sessions and his/her family bringing medicine to school (see SN checklist)
AIM 1: Secondary Asthma Health Outcomes	
Asthma symptoms	
 Asthma Control Test (see Parent surveys), validated maximum symptom days, validated
ED visits, Admissions, Oral steroids, Medication Adherence	
 Parent report (see Parent surveys) and electronic medical record review Pharmacy refill data
Spirometry	
 Portable Spirometer (PIKO), validated⁵⁷ to assess Forced Expiratory Volume in 1sec
School absences	
 Parent and school nurse report (see Parent surveys and SN checklist)
AIM 2: Process Outcomes for Asthma Link™ Intervention Protocol	
Acceptability	
 Acceptability rating scale (5 point Likert scale) to rate each component of the Asthma Link™ intervention (see Parent, SN, MP, AC surveys)

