11. PROCEDURES INVOLVED*

Randomization. Two groups of two practices (4 practices in total) will be matched based on comparable size and percent of minority patients. Within each pair, practices will be randomly allocated to Asthma Link or the comparison condition, using a computerized function. This will result in two practices randomized to the Asthma Link condition and two practices randomized to the Enhanced Usual Care comparison condition.

Recruitment will be performed from each practice site until the target n=72 parent-child dyads (18 per site) are recruited. (see section 13 on “Sample size calculation”) Recruitment will begin during the 2021-2022 academic school year.

Procedure Steps:

1. Research coordinator (RC) identifies potentially eligible patients (children aged 6-17 years (enrolled in grade 1-12) years and prescribed a daily inhaled corticosteroid per medical record from most recent visit scheduled for a clinic visit) through the practice's office scheduling and medical record system (e.g., Epic). RC will also collect that patient's name, DOB, mailing and email addresses, phone number, insurance type (as a proxy for socioeconomic status), list of

INVESTIGATOR STUDY PLAN

medications, number of emergency room visits, number of hospital admissions and number of oral steroid courses for asthma relief.

2. RC creates a Lilac Form for any potentially eligible patients as described above. (Lilac form is an indicator to the medical provider seeing the patient that this patient is potentially eligible for study.)

3. Asthma Link condition: As part of clinical practice, medical provider will determine if patient is struggling with taking daily asthma medicine. If YES, then will introduce Asthma Link by saying “There is a clinical program that allows for your child to receive their daily asthma medicine at school supervised by the school nurse.” Child can be enrolled in Asthma Link per the usual clinical steps (see Asthma Link steps).

- After they are enrolled in Asthma Link, medical provider will give family one-page description of study (see Flyer) and state “Researchers at UMass are performing a study of children who are participating in Asthma Link, would you be interested in hearing more?”

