3a. Enhanced Usual Care comparison condition: Medical provider will determine if patient is struggling with taking daily asthma medicine, if YES, the provider will give family a one-page description of study (see Flyer) and state “Researchers at UMass are performing a study of children with asthma to learn about how to support them in taking their every day asthma medicine, would you be interested in hearing more?”

- Attached to the “Flyer” will be the Authorization to Contact form. (see Authorization to Contact form)
- If the parent agrees, the Lilac form with the family’s information is faxed to the Research Coordinator. The pediatric office will fax this form with a confidential cover form.
- The fact sheet will be mailed to the parent with a letter saying that the Research Coordinator will call or text them (see Fact Sheet).
- The Research Coordinator will only call the parent five times. The first and third time a message will not be left, but a text message will be sent stating “This is X from Asthma Link, can I call you at TIME?” The second, fourth, and fifth time a message will be left saying “This is X from the University of Massachusetts Medical School. I am calling about the material on Asthma Link I sent you. Please call me back at X.”
- A phone screen will be conducted to ensure study inclusion criteria (see phone script).
- The Research Coordinator will obtain informed consent from eligible participants, including parental permission for their child to participate, child assent to participate, and parental consent to participate. (see sections 30, 31 on Consent)
- After all questions are answered regarding the study by the parent, the Research Coordinator will send the baseline survey via email to the participant to be completed by the parent and child together or will complete the survey over the phone with the child and parent.
- The Research Coordinator will then access the child’s medical record and obtain the discharge summaries, the emergency service records, the office/clinic notes, the problem list, the pulmonary studies, the child’s list of medications, and the child’s height and weight (to help interpret the spirometry data).
- The Research Coordinator will then call the child’s pharmacy to obtain refill history for their daily ICS inhaler.

INVESTIGATOR STUDY PLAN

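### Practice-record events are described only as counts per window and the analysis names neither source nor baseline count, so uneven record capture can bias a crude arm comparison (minor)

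*Combined protocol and SAP*

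**What the plan says.** Section 10 names two sources for ED visits, admissions and oral steroids: "Parent report (see Parent surveys) and electronic medical record review". Section 11 puts these events in all four parent surveys (baseline, 3, 6 and 12 months).

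For the record, section 11 states: "We will be accessing the practice's medical record system (same system as above, e.g., Epic) to obtain documentation of the child's emergency room visits", and likewise for admissions and steroid courses. At baseline the form of the data is "recording the number of events for the 6 months prior), 3 month, 6 month, and 12 month time points"; at follow-up it is "recording the number of each of these events for the 3 or 6 months prior". Entry is immediate: "This data will be directly put into the RedCap database without any downloading of information". This text mentions no event date, no source field and no marker that the event was for asthma. The record and the pharmacy are consulted once more, 12 months after the 12-month survey; no parent survey is listed for that time.

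After the baseline survey the coordinator is also to "access the child’s medical record and obtain the discharge summaries, the emergency service records, the office/clinic notes".

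On allocation, section 11 says: "Within each pair, practices will be randomly allocated to Asthma Link or the comparison condition". This gives two practices per arm, with a target of 18 dyads in each. Section 13 plans a t-test, a nonparametric equivalent or Poisson regression, without naming a term for practice, source or baseline count. It calls the health-outcome analyses exploratory. No section says which source counts or how the two are reconciled.

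**The concern.** A practice's record may hold an outside ED visit only if word of it reaches the practice. How often that happens is a property of the practice, and each practice lies wholly in one arm. If capture differs, the record-based event rates differ between arms even when the true rates do not.

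Two features add to this. First, section 5 describes continuing contact among practice, school nurse and family as part of Asthma Link, so capture could rise in that arm alone once the program starts. Second, a count cannot be matched to another count: one ED visit in the survey and one in the record may be one visit or two.

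The cost falls mainly on the next trial. Section 13 carries the ICC, standard deviation and effect size forward to its sample size, and uneven capture between practices would distort the ICC of record counts as well as the arm contrast.

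**Working it through.** The plan states no figure on capture, so there is none to reproduce. From the documents: 2 practices per arm, 18 dyads per practice (36 per arm), a 6-month baseline window and 12 months of follow-up. Capture fractions, event rates and parent reporting rates are assumptions throughout.

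**1. Crude comparison, no true effect.** The recorded rate ratio equals capture under Asthma Link divided by capture under comparison:
- 0.9/0.8 = 1.13
- 0.9/0.7 = 1.29
- 0.9/0.6 = 1.50

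**2. Stable capture, follow-up relative to baseline.** The same factor appears in both periods: (0.9/0.7)/(0.9/0.7) = 1.00. Simulated Poisson counts for 4 practices of 18 children agree. The crude ratio is 1.29 and the ratio relative to the baseline record count is 1.00. Parent report, assumed equally complete in all practices, also gives 1.00.

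**3. Capture varying at random between practices.** This is the simulated false-positive rate of a crude two-arm Poisson comparison that ignores practice (nominal 5%), with capture centred on 0.8:

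| Events per child-year | log-SD 0 | 0.1 | 0.2 | 0.3 |
|---|---|---|---|---|
| 0.5 | 3.8% | 4.8% | 5.8% | 7.1% |
| 1 | 4.5% | 6.3% | 9.3% | 12.5% |
| 2 | 4.6% | 7.7% | 14.6% | 20.4% |

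Relative to the baseline count, the rate stays between 3.5% and 4.9% throughout, provided capture does not change over time.

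**4. Price of that correction.** At 1 event per child-year and capture 0.8, expected recorded events per arm are 36 × 1 × 0.8 = 28.8 in follow-up and 36 × 0.5 × 0.8 = 14.4 at baseline. The standard error of the log rate ratio is √(2/28.8) = 0.26 for the crude comparison and √(2/28.8 + 2/14.4) = 0.46 relative to baseline.

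**5. Capture that shifts after randomization in one arm.** Let capture be 0.7 in both arms at baseline, then 0.9 under Asthma Link and 0.7 under comparison. Relative to baseline the ratio is (0.9/0.7)/(0.7/0.7) = 1.29, so the baseline count removes nothing. A true ratio of 0.7/0.9 = 0.78 would be recorded as 1.00.

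**6. Counting an event found in either source.** Let parents report a fraction p. If the sources are independent, combined capture is 1 − (1 − c)(1 − p):
- p = 0.6: 0.96/0.88 = 1.09
- p = 0.8: 0.98/0.94 = 1.04

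Under maximum positive dependence, combined capture is max(c, p):
- p = 0.6: 0.9/0.7 = 1.29
- p = 0.8: 0.9/0.8 = 1.13

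Merging therefore helps much, little or not at all, depending on a dependence that undated counts cannot show.

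**The case against.** A reader might infer that capture is inseparable from treatment in this design. The documents do not support that. The same record is counted for the 6 months before baseline, which cancels stable differences (step 2). Parent report covers the same events at four times in every practice. Per-child counts from two sources already allow agreement to be compared by practice, so the pilot can say something about which source a larger trial should use.

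A reader might also infer that only counts will exist. That is not established. The coordinator obtains discharge summaries and emergency records, and the survey and REDCap forms are cited as uploads without being reproduced. What stands is that section 11 describes the recorded item as a number, with no date. Section 14 destroys the link between identifiers and data at study completion, so matching could not be rebuilt from charts after that.

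A third inference would be that uneven capture would mimic benefit, for instance 0.60/0.85 = 0.71. That needs the poorer capture to lie in the Asthma Link practices. The only arm-specific mechanism the documents suggest, closer contact, points the other way. Nor do they say that the four practices, all in one city, differ in capture.

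Two general objections carry weight. With two practices per arm, every practice trait is confounded with arm, not only record capture. And section 13 disclaims meaningful effect estimates from a pilot of this size. Both limit the importance of the point without removing it.

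**Conclusion.** The point holds in a limited form. A crude record-based comparison, which section 13 leaves open, mixes capture with treatment. The baseline count deals with differences that are stable, at a cost in precision. It does not deal with a shift in one arm after randomization, where assumed capture of 0.9 against 0.7 gives a false ratio of 1.29 and would hide benefit.

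Parent report is the available cross-check. It is weakened because parents know which program their child receives, because undated counts cannot be matched, and because no parent survey is listed at the last collection. Every capture, event and reporting rate used here is assumed. Since the outcomes are secondary and exploratory, this is a minor improvement and not a flaw in the trial's main purpose.

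**What to change.** - In section 11, replace the count per window with one REDCap line per event: date, type (ED visit, admission, oral steroid course), for asthma yes or no, and source. Ask parents for an approximate date.
- Keep parent and record data as separate fields. In section 13, analyse each source with adjustment for its own baseline count. The cancellation in step 2 is for follow-up rate relative to baseline rate (an arm-by-period term in a Poisson model). A child's baseline count entered as a covariate would generally remove only part of a practice-level difference.
- Report parent–record agreement by practice.
- Give the merged either-source count as a sensitivity analysis only, because it assumes something about dependence and brings in unblinded report.
- State that the record data collected 12 months after the 12-month survey have no parent cross-check.

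The cost is a few more minutes for each child with events, and a small revision to the parent survey that needs IRB approval. The coordinator already opens the records concerned.
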